2. GENERAL ANALYSIS DEFINITIONS

2.1. Visit Windows

The primary endpoint of this study is the MRD conversion rate from baseline to 12 months after initiation of maintenance treatment. As subjects do not always adhere to the protocol visit schedule, a 2-month window is extended to 12-month MRD assessment for the primary endpoint.

For analyses of data by cycle, if data are collected by date (e.g., AE onset), the corresponding study evaluations will be assigned to actual sequential cycles, which are derived from the study treatment administration data. The start date of a certain cycle is defined as the date of the first scheduled dose of any component of the study treatment, and the end date of a cycle is the start date of the next cycle minus 1. For the last cycle, the end date is defined as the end of treatment

visit date, or the minimum of last study treatment date plus 30 days and subsequent antimyeloma therapy minus 1 day if the end of treatment visit date is not available.

In general, if data (e.g., laboratory, vital sign and PRO etc.) are collected by cycle, the nominal cycle will be used to summarize data. However, due to possible cycle delays, assessment performed in the same cycle may not be well aligned in time scale for different subjects. If a subject has 2 or more actual visits in the visit window, the visit closest to the target day will be used as the protocol visit for that visit window.

2.2. Pooling Algorithm for Analysis Centers

All participating centers in the study will be pooled together for analyses.

2.3. Analysis Sets

2.3.1. Efficacy Analysis Set(s)

The full analysis set (FAS), following the intent-to-treat principle, includes all subjects randomly assigned to daratumumab in combination with lenalidomide or the lenalidomide alone. Analyses of demographics, baseline characteristics, and efficacy endpoints will be analyzed based on this analysis set.

MRD evaluable analysis set includes all randomized subjects who have MRD assessment at baseline and have at least one post-baseline MRD evaluation. The MRD evaluable analysis set will be used for supplementary analysis of the primary endpoint MRD conversion by 12 months.

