5.2.1. Definition

The primary endpoint of this study is the MRD conversion rate from baseline to 12 months after start of maintenance treatment. It is defined as the proportion of subjects who were MRD [at 10⁻⁵] positive at baseline and have achieved MRD negative status [at 10⁻⁵] as determined by NGS by 12 months of maintenance treatment. The primary endpoint will be analyzed based on FAS.

Subjects' MRD positive status at baseline should be verified. Since subjects do not always adhere to the protocol visit schedule, the post-baseline MRD records from randomization up to 12-month + 2 months will be selected for MRD negativity status evaluation. Subjects with missing or unevaluable MRD status will be considered as MRD positive. Subjects who have achieved MRD negative status on or after PD or switch to subsequent anti-myeloma therapy before PD, will not be considered MRD negative in the primary endpoint analysis.

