5.2.3. Analysis Methods

The MRD conversion rate will be calculated for each treatment group based on the FAS. The corresponding 95% exact CI will be provided.

The stratified Cochran-Mantel-Haenszel (CMH) method will be used to test if the MRD conversion rate is the same between the two treatment groups. Stratification factor included in the analysis is baseline cytogenetic risk per investigator's assessment (high risk versus standard/unknown risk) as used for randomization of the study. The estimate of odds ratio and its 95% confidence interval will be provided. P-value will be provided by Fisher's exact test.

The following supplemental analyses may be performed in a similar manner as described above:

- MRD negativity conversion rate (10-5) by 12-months for the MRD-evaluable analysis set
- MRD negativity conversion rate (10-5) by 12-months for subjects in FAS who achieved CR or better response per computerized algorithm at any time during the study
- MRD negative (10⁻⁵) CR conversion rate by 12 months of maintenance treatment in FAS where MRD negative CR conversion rate is defined as the proportion of subjects achieved MRD negativity and CR or better response by 12-months of maintenance treatment according to IMWG criteria per computer algorithm
- MRD negativity rate at 10⁻⁴, 10⁻⁵ and 10⁻⁶ by 12 months of maintenance treatment in FAS
- MRD negativity (10⁻⁵) conversion rate by 12-months of maintenance treatment by subgroups of subjects according to Section 2.4. Analysis will be performed similarly as

the primary analysis except that randomization stratification factor will be excluded from CMH test. Forest plot will be generated.

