5.4.1. Definition

MRD by NGS are evaluated post-baseline at the end of 12, 18, 24, and 36 months after the start of study treatment(s). The overall MRD negativity (10^{-5}) conversion rate at any time after randomization is defined as the rate of MRD converted from positive at baseline to negativity at the threshold 10^{-5} achieved at any time after randomization.

In addition, MRD negativity (10^{-5}) conversion rate at 12, 18, 24 and 36-months landmark time with +/- 2 months window, as well as accumulative rate up to these timepoints will be summarized. MRD negativity (10^{-5}) CR conversion rates for FAS patients, and MRD negativity (10^{-5}) conversion rates for those achieved CR or better response per computerized algorithm will be summarized in a similar manner.

Durable MRD (≥ 1 year) negativity rate, defined as the proportion of subjects who have achieved MRD negative status (at 10⁻⁵) in 2 bone marrow aspirate examinations that are a minimum of 1 year apart, without any examination showing MRD positive status in between assessments. Subjects who have achieved MRD negative status on or after PD or switch to subsequent antimyeloma therapy before PD, will not be considered MRD negative. Subjects with missing or unevaluable MRD status will be considered as MRD positive.

Similar analysis will be performed for durable MRD (≥6 months) negativity rate.

OS, measured from the date of randomization to the date of the subject's death due to any cause. Subjects who died after consent withdrawal will be considered as having an OS event. Subjects who are lost to follow-up will be censored at the time of lost to follow-up. If the patient is alive and vital status is unknown, then the patient's data will be censored at the date the patient was last known to be alive determined by the maximum collection/assessment date from among selected data domains within the clinical database.

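### The MRD-evaluable set has no upper time limit, so the 12-month supplementary analysis does not fully remove the missing-equals-positive imputation it is there to relax

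*SAP*

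**What the plan says.** SAP 2.3.1 defines the set: "MRD evaluable analysis set includes all randomized subjects who have MRD assessment at baseline and have at least one post-baseline MRD evaluation". It gives the set one purpose: "The MRD evaluable analysis set will be used for supplementary analysis of the primary endpoint MRD conversion by 12 months". There is no latest date for the qualifying evaluation.

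SAP 5.2.1 defines the endpoint on a bounded window: "the post-baseline MRD records from randomization up to 12-month + 2 months will be selected for MRD negativity status evaluation". It adds: "Subjects with missing or unevaluable MRD status will be considered as MRD positive". It also asks that baseline positivity be verified, whereas the set requires only a baseline assessment.

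SAP 5.2.3 lists the analysis under the sentence "The following supplemental analyses may be performed in a similar manner as described above", as "MRD negativity conversion rate (10-5) by 12-months for the MRD-evaluable analysis set".

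SAP 5.4.1 and the protocol's Time and Events Schedules place post-baseline MRD samples at 12, 18, 24 and 36 months (C13D1, C19D1, C25D1 and the end-of-treatment visit). Aspirates within 30 days either side of a maintenance visit are accepted.

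**The concern.** Membership of the set and the scoring of the endpoint run on different clocks. A patient whose C13D1 sample was missed, and whose first post-baseline sample is an MRD-negative one at C19D1, meets the membership rule. The endpoint cannot read that sample. If the missing-data rule applies, the patient sits in an analysis labelled evaluable and is counted as not converted, although nothing was measured in the window.

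Among the supplementary analyses in SAP 5.2.3, this is the only one that relaxes the missing-equals-positive rule. The others change the response requirement, the MRD threshold or the subgroup. In an open-label trial, missing marrow samples could differ by arm, and this is the analysis a reader would use to judge how much that matters.

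**Working it through.** **Plan's own figure.** SAP 1.4 states at least 85% power for 40% versus 20%, 107 per arm, two-sided 0.05, continuity-corrected chi-squared. The pooled rate is 0.30, the null SE √(0.21 × 2/107) = 0.0627, the alternative SE √((0.24 + 0.16)/107) = 0.0611, and the correction 1/107 = 0.0093. Then z = (0.20 − 0.0093 − 1.96 × 0.0627)/0.0611 ≈ 1.11, which gives 86.6% power. The figure reproduces, and this point does not touch it.

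**Can a sample qualify a patient yet never count?**
- Month 14: 14 × 30.4375 = about day 426.
- C19D1: 18 × 28 + 1 = day 505; with the 30-day tolerance, day 475 at the earliest.
- So an on-schedule 18-month sample always admits the patient to the set and always falls outside the endpoint window.

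**Are such samples present at the primary analysis?** The SAP plans one year of accrual (1.4) and runs the analysis once all patients have completed 12 months of treatment or stopped (3). Assume uniform accrual and a cut when the last patient reaches C13D1. C19D1 is 6 × 28 = 168 days later, so (365 − 168)/365 = 54% of patients would already have reached it. With the cut 12 months after the last randomization, the share is 50 to 62%, depending on whether the visit is counted as 18 calendar months or as day 505.

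**Effect on rates, balanced case.** Let m be the share with no result by month 14 (assumed, same in both arms), and suppose all who have reached C19D1 are sampled there. Displayed rate = p(1 − m)/[(1 − m) + 0.54m].

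| m | Patients re-entering (214 × m × 0.54) | 40% shows as | 20% shows as | Odds ratio |
|---|---|---|---|---|
| 5% | about 6 | 38.9% | 19.4% | 2.64 |
| 10% | about 12 | 37.7% | 18.9% | 2.61 |
| 15% | about 17 | 36.5% | 18.3% | 2.58 |

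A set limited to patients with a result by month 14 would show 40% and 20%, odds ratio (0.40/0.60)/(0.20/0.80) = 2.67.

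**What the set does remove.** Illustration per arm: 10 never sampled after baseline, 5 sampled only after month 14, 92 with a result in the window. Converters are 0.40 × 92 = 36.8 and 0.20 × 92 = 18.4.
- Full analysis set (107): 34.4% versus 17.2%.
- Set as written (97): 37.9% versus 19.0%.
- Time-limited set (92): 40.0% versus 20.0%.

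The set removes 10 of the 15 imputed cases and keeps 5.

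**Unbalanced case.** Again 10 never sampled per arm, so 97 in the set per arm.
- Late-only 10 on the combination, 2 on lenalidomide alone: 0.40 × 87/97 = 35.9% versus 0.20 × 95/97 = 19.6%, odds ratio 2.30.
- Late-only 2 and 10: 0.40 × 95/97 = 39.2% versus 0.20 × 87/97 = 17.9%, odds ratio 2.95.

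**The case against.** Several points on the other side stand.

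- A reader might infer that the set fails to remove the imputed cases at all. It does not fail to that extent: anyone with no post-baseline MRD evaluation is excluded.
- A reader might infer that the rate drifts with each data cut. No such re-run is planned. The annual updates in protocol 11.6 concern secondary endpoints and safety, and this set serves only the primary endpoint.
- A reader might count patients whose only sample was unevaluable as kept too. That depends on whether an unevaluable sample is an evaluation. The SAP does not say, and excluding it is at least as natural.
- Carry-over of the missing-data rule is an inference. The rule sits in 5.2.1, in a definition tied to the full analysis set; the similar-manner sentence in 5.2.3 follows the test methods.
- The tabulated rates are near an upper bound for that cut. Patients who stop treatment early have no scheduled C19D1 sample. Their end-of-treatment sample, if taken, often falls inside the window, and with no sample they are excluded.
- SAP 5.4.1 reports 12- and 18-month landmark, cumulative and any-time conversion, so a late negative result is visible elsewhere.

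None of this supplies the missing time limit. If the rule does not carry over, the SAP leaves unstated how a late-only patient in the set is to be counted. The landmark summaries do not replace an evaluable-set analysis of the 12-month endpoint.

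**Conclusion.** The mismatch is in the text and no other section resolves it: membership is open-ended, while the endpoint closes at 12 + 2 months. Read in the most natural way, the analysis keeps some patients as non-converters by imputation and so removes that imputation only in part.

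The consequence is limited. Under assumed missingness of 5 to 15%, equal in both arms, the displayed rate falls by about 1 to 3.5 points from 40% and by 0.6 to 1.7 points from 20%, and the odds ratio goes from 2.67 to about 2.6. A material shift in the odds ratio needs late-only patients to be unbalanced between arms, for which the documents give no evidence either way. The sizes also rest on uniform one-year accrual and on the missing rule carrying over. The primary test on the full analysis set, its alpha and the sample size are unaffected, and the supplementary analysis is itself optional. It is worth correcting because the label promises something that the definition does not deliver.

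**What to change.** In SAP 2.3.1, define the set as randomized subjects with a verified MRD-positive baseline at 10⁻⁵ and at least one evaluable (positive or negative) post-baseline NGS result dated from randomization to 12 months + 2 months. Add that subjects with progression or subsequent anti-myeloma therapy before such a result stay in the set as non-converters. Without that sentence the tighter definition could drop them, against the composite strategy in SAP 5.2.2.

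This also aligns the baseline condition with 5.2.1 and settles whether an unevaluable sample qualifies. The cost is SAP wording and a slightly smaller set; no new data or visits are needed.

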2.3.2. Safety Analysis Set

The safety analysis set includes all randomized subjects who received at least 1 dose of study agent.

2.4. Definition of Subgroups

The pre-specified subgroups are summarized in **Error! Reference source not found.** Additional exploratory subgroup analyses may be performed, if requested and deemed necessary by IDMC for their analyses and decision making.

Table 1: Subgroup Definition

Subgroup	Definition of Group	Analysis Type
Sex	MaleFemale	E, S
Age	• <65, 65-<70, ≥70 years	E, S
Race	• White, Black or African American, Other	E, S
Baseline renal function	 <60 mL/min 60 to <90 mL/min ≥90 mL/min Based on creatinine clearance (mL/min) values 	S
Baseline body weight	 ≤70 kg >70 kg 	Е
Baseline ECOG performance score	$\begin{array}{ccc} \bullet & 0 \\ \bullet & \geq 1 \end{array}$	Е
International Staging System (ISS) at diagnosis	• I • II • III	E
Cytogenetic risk at screening	 High-risk ^a Standard-risk/unknown 	Е
Revised cytogenetic risk at screening	 High-risk ^b Standard-risk/unknown 	Е
Cytogenetic risk at MM diagnosis	 High-risk ^a Standard-risk/unknown 	E
Revised Cytogenetic risk at MM diagnosis	 High-risk ^b Standard-risk/unknown 	E

E= efficacy (MRD negativity rate, PFS, CR or better rate), ECOG= Eastern Cooperative Oncology Group, S=Safety

^a Cytogenetic high risk is defined as positive by FISH/Karyotype testing of subjects having t(4; 14); t(14; 16) and/or 17p deletion.

^b Revised cytogenetic high risk is defined as positive by FISH/Karyotype testing of subjects having t(4; 14); t(14; 16), 17p deletion, t(14; 20) and/or gain/amp1q.

Note: t(14; 20) is only available for local lab, and unavailable for central lab.

2.5. Study Day and Relative Day

Study Day 1 refers to the date of first study treatment administration. All efficacy and safety assessments at all visits will be assigned a day relative to this date.

Study day or relative day for a visit is defined as:

- Visit date (Date of Study Day 1) +1, if visit date is \geq date of Study Day 1
- Visit date Date of Study Day 1, if visit date is < date of Study Day 1

2.6. Baseline

The baseline value is defined as the closest non-missing value on or prior to the first study treatment administration (including time if time is available, with exception of parameters associated with disease-related efficacy assessment).

2.7. Unique Lab Value

In general, in instances when there are multiple records at a given visit date for laboratory parameters, the following rules are applied to select the unique laboratory value for analysis:

a) When there are multiple records from both central and local labs, central lab value always takes precedence over local lab value

b) When there are multiple records from central lab for a treatment phase, select the latest value as the unique lab value within the treatment phase

c) When there are multiple records from local lab for a treatment phase, select the latest lab value as the unique lab value within the treatment phase with the exception of cytogenetic risk at diagnosis where the earliest local lab data is used.

Cytogenetic risk is to be determined using data from central or local labs. Local lab data was only used in case of unavailability of central lab data for all the genes defining high risk. No mixture of central and local cytogenetic data was done to define high cytogenetic risk status for a subject.

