Cytogenetics - FISH aspirate (performed centrally)	X	-	_	-	 Central cytogenetics assessment is not required during screening if local laboratory assessment included del(17p), t(4;14), and t(14;16) performed as part of standard of care at any time from the time of diagnosis of multiple myeloma to randomization. Central FISH testing to include del(1p), gain of 1q, del(17p), t(11;14), t(4;14), t(14;16), and t(14;20). Any existing cytogenetics results from the local laboratory, if available, should be entered in the eCRF. Note: Stratification will be based on central laboratory results or local laboratory results, if available. For stratification purposes, if central cytogenetic results are not available (ie, due to technical reasons), or if central cytogenetic results, then local cytogenetic my be used with the approval of the medical monitor. If central and local cytogenetic results are unavailable, the patient will be stratified with patients with standard cytogenetics.

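### For revised cytogenetic risk at screening, SAP 2.7 and SAP Table 1 conflict: t(14;20) defines high risk and is said to come only from local laboratories, but local results may not be used or combined once central results exist

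*SAP*

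**What the plan says.** **Definition.** SAP 2.4, Table 1, footnote b: "Revised cytogenetic high risk is defined as positive by FISH/Karyotype testing of subjects having t(4; 14); t(14; 16), 17p deletion, t(14; 20) and/or gain/amp1q". The note beneath the footnotes reads: "Note: t(14; 20) is only available for local lab, and unavailable for central lab".

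**Source rule.** SAP 2.7 states that, for multiple records at a visit, "central lab value always takes precedence over local lab value". On cytogenetic risk it adds "Local lab data was only used in case of unavailability of central lab data for all the genes defining high risk" and "No mixture of central and local cytogenetic data was done to define high cytogenetic risk status for a subject". For local records it takes the latest value in a treatment phase, "with the exception of cytogenetic risk at diagnosis where the earliest local lab data is used".

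**Central panel.** The cytogenetics row of the protocol's Time and Event Schedule, Part 1, lists seven abnormalities for central testing ("Central FISH testing to include del(1p), gain of 1q, del(17p), t(11;14), t(4;14), t(14;16), and t(14;20"). Part 2 gives the same list.

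**Waiver of central testing.** The same row lets a patient skip central FISH when a local test covered three markers ("Central cytogenetics assessment is not required during screening if local laboratory assessment included del(17p), t(4;14), and t(14;16"). That local test may date from any time between diagnosis and randomization. Protocol 9.3.4 repeats the waiver and sends the second aspirate for central cytogenetics only if no local evaluation was done.

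**The concern.** The definition needs a marker that, according to the SAP, the preferred laboratory does not supply. The source rule then closes off the laboratory that does. A patient with a documented high-risk lesion can therefore be counted as standard/unknown, and in the cases below the shift is always in that direction.

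Cytogenetic risk and revised cytogenetic risk at screening are pre-specified efficacy subgroups for MRD negativity, PFS and CR or better, with forest plots (SAP 2.4, 5.2.3, 5.3.2, 5.4.1). Both also appear in the baseline characteristics (SAP 4.1, Table 3). Because the condition for using local data is ambiguous, two programmers could follow SAP 2.7 faithfully and produce different subgroups.

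**Working it through.** The plan gives no figure to reproduce; the check is of a classification rule.

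**Inputs.** The five revised markers are t(4;14), t(14;16), del(17p), t(14;20) and 1q gain (SAP 2.4). Central testing is taken to cover all of these except t(14;20), as the SAP note says. A local panel covers either the three markers needed for the waiver or all five.

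**Two readings of the condition in SAP 2.7.**
- Reading A: local data are used only when central testing gave no result for any of the markers.
- Reading B: local data are used whenever the central result is incomplete for the set of markers.

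Under B, and on the SAP's own note, central data are never complete for the revised definition. Local data therefore replace them wherever local data exist.

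| Available results | Abnormality present | Reading A | Reading B |
|---|---|---|---|
| Central + five-marker local | t(14;20) only | standard/unknown | high |
| Central + three-marker local | 1q gain only | high | standard/unknown |
| Central + five-marker local | t(14;20) and 1q gain | high | high |
| Partial central (del(17p) negative, other probes failed) + local | t(4;14), found locally | standard/unknown | high |
| Central only | 1q gain only | high | high |
| Five-marker local only | t(14;20) only | high | high |
| Three-marker local only | t(14;20) only or 1q gain only | standard/unknown | standard/unknown |

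The first, second and fourth rows are the defect: a positive result is on file and one reading discards it. The fourth row also misclassifies under the three-marker definition, but only under Reading A. The last row is a different matter, since the marker was never tested.

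**If the protocol is right about the central panel.** A complete central result then covers all five markers. The t(14;20) loss under A and the 1q loss under B both disappear for such patients, and only partial central results remain a problem.

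**Illustrative size for t(14;20), Reading A.** Number = 214 × share with central data × prevalence of isolated t(14;20). Only 214 is in the documents.
- Low: 214 × 0.50 × 0.01 = 1.1.
- High: 214 × 1.00 × 0.02 = 4.3.
- Central FISH as a fallback, 25% share: 214 × 0.25 × 0.01 = 0.5, to 214 × 0.25 × 0.02 = 1.1.
- Wider range: 214 × 0.25 × 0.005 = 0.3, to 214 × 1.00 × 0.05 = 10.7.

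Each figure also supposes that every such carrier has a local t(14;20) result that counts towards screening, so the true number can only be lower for a given prevalence and share.

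**The case against.** The strongest defence is that few patients are exposed. Under the protocol, central FISH is waived when a qualifying local result exists, so central testing is largely a fallback. Patients with only one source are untouched by the precedence and no-mixing rules. This stands, and it pulls the count towards the low end.

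Second, classifying each patient from one laboratory is a legitimate choice. That also stands as a principle, but a single-source rule must be able to apply the definition it serves. Here the SAP's own note says that central data cannot.

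Third, the confirmatory analyses are safe. The CMH test and the main PFS analysis use the randomization factor (SAP 5.2.3, 5.3.2), which rests on three markers (protocol section 5). The MRD and PFS subgroup analyses are optional supplementary work with the stratification factor removed. This stands in full.

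Three stronger readings are tempting, and the documents do not support them:
- A reader might infer that revised risk can never be derived. It can: a five-marker local panel classifies correctly when there is no central result, and a t(14;20) carrier with another counted marker remains high risk. Central FISH is scheduled at screening only and the diagnosis subgroups draw on local records, so those subgroups escape the conflict.
- A reader might multiply an assumed central failure rate by an assumed share of high-risk patients and report a larger count. The documents give neither rate. The product also presumes that everyone has central FISH, that the failed probe is the one that would have been positive, that no other marker is positive, and that a local positive is on file.
- A reader might suppose that this is the subgroup in which the treatment effect is most in doubt. Nothing in either document says so.

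**Conclusion.** The point holds, narrowly. SAP 2.4 and SAP 2.7 are inconsistent for revised risk at screening, and the SAP note on t(14;20) contradicts the protocol's central panel. Under Reading A, isolated local t(14;20) is discarded when central data exist, and so is a local positive on a marker that failed centrally; the latter also affects the three-marker screening subgroup. Under Reading B, an isolated central 1q gain is discarded when a three-marker local panel exists.

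Only patients with both sources are affected. For t(14;20), about 1 to 4 of 214 is an illustration resting on assumed prevalence of 1 to 2% and central data in 50 to 100%. The documents give no basis for counting the partial-result or 1q cases. The consequence is confined to the screening-risk efficacy subgroups and the baseline table. No conclusion on the primary endpoint or the main PFS comparison changes. It is worth correcting because the correction is cheap and the present text does not determine the subgroup.

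**What to change.** 1. Establish whether the central laboratory reported t(14;20), and bring the note under SAP Table 1 into line with the protocol's Time and Event Schedule, Parts 1 and 2.
2. Replace the last two sentences of SAP 2.7 with a marker-level rule applied separately at screening and at diagnosis. High risk: any listed marker positive from either laboratory. Standard: all listed markers tested and negative. Unknown: anything else. A positive from either source must count; putting central first for each marker would still let a central negative override a documented local positive.
3. State which sample dates belong to each time point, since a local result may date from any time between diagnosis and randomization.
4. Report the number of patients who are unknown because a marker was not tested. They can stay pooled with standard risk in the subgroup analyses as now, but SAP Table 3 currently shows only standard and high.

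The cost is SAP wording and a re-derivation from data already collected, since the protocol has local cytogenetic results entered in the eCRF. The small downside is that results from two laboratories are combined within a patient.
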